Likely contributors to above measures: Lipid/glucose markers:(fasting C-peptide and lipid panel, HbA1c); hepatic markers:(c-reactive protein, glucagon, GLP-1 and leptin at baseline, 5 min and 30 min post glucose load to asses change with OG, adiponectin, AST, ALT, GGT), sex-steroids:(DHEAS, free and total testosterone, sex hormone binding globulin, progesterone, estradiol); Body size and composition: (BMI, waist/hip ratio, DEXA, hepatic visceral fat via MRI³⁶⁻³⁹), Whole body fat oxidation at rest and following glucose ingestion as measured with a metabolic cart; Physical activity/ diet:(accelerometer, activity survey (3DPAR); Food frequency survey).Questionnaires for presence of obstructive sleep apnea. Questionnaires for perceived mental strengths and difficulty (note there is no assessment of suicidality on this tool). Obstructive Sleep Apnea, to be assessed with an overnight sleep study via WatchPAT.

B. Description of Population to be Enrolled:

Study staff aims to enroll 20 obese girls with regular menstrual cycles, 20 girls with un-treated PCOS, 20 girls with PCOS treated with at least 6 months of Metformin and 20 girls with PCOS treated with at least 6 months of oral contraceptives. The PCOS groups will be compared to 20 obese non-PCOS controls. This is the number of participants needed to be completed statistically, thus more subjects may be enrolled, to allow for screen failures and dropouts. Total enrollment will be up to 100 participants.

Ethnic Categories	Gender		
	Females	Males	Total
Hispanic or Latino	40	0	40
Not Hispanic or Latino	60	0	60
Ethnic Categories: Total of All Subjects	100	0	100
Racial Categories			
American Indian/Alaska Native	5	0	5
Asian	10	0	10

Native Hawaiian or Other Pacific Islander	10	0	10
Black or African American	32	0	32
White	43	0	43
Racial Categories: Total of All Subjects*	100	0	100

Inclusion Criteria:

- 1) Female
- 2) Ages 12-21
- 3) Sedentary- less than 2.5 hours of moderate (jogging, swimming etc) exercise a week.
- 4) BMI equal or greater than the 90th percentile for age and gender
- 5) For PCOS groups: (NIH definition) irregular menstrual cycles at least 1.5 years after menarche and either clinical evidence of hyperandrogenism or elevated Testosterone (above the norms for age/tanner stage) at time of screening or documented prior to initiation of therapy for OCP and metformin groups.

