Power calculation: The primary outcome is hepatic substrate flux pathway percentages measured as PEP, TCA and TG synthesis pathways. Power analysis is based on publications utilizing similar methods, with the Primary Aim of understanding differences in hepatic metabolism in obese girls with PCOS who either have or do not have hepatic steatosis. The reference manuscript included 13 men without HS, and 6 men with HS⁵⁰. They found that during hyper-insulinemia, glycerol related gluconeogenesis was increased, as was the PEP cycle in individuals with HS compared to those without. Utilizing the PEP value, from this paper, the difference between the group means is 3 μ mol.min.kg FFM, and the standard deviation is 2 μ mol.min.kg FFM. Differences between the two primary groups (PCOS, controls) will be assessed with a t test or for non-normally distributed data a non-parametric test such as Mann-Whitney U. With 15 untreated PCOS with HS and 15 untreated PCOS without HS, we would have a power of 0.97 to detect an alpha of 0.05. Since the reference population is men who have more uniform hormone profiles, I am choosing to be overpowered should the variability in our population be greater. As the measurement is in kg of fat free mass, we will not have to do adjustments with BMI or weight. However, as African Americans are less likely to have HS, and Hispanics more likely to have HS, if ethnicity percentages are different between groups, we will need to adjust for ethnicity in our calculations.

Secondary Aims: a) For comparison of the PCOS to control groups, individuals will be matched in terms of HS status, so that the comparison is just between the hormonal state. I am assuming that there will be less of a difference between these groups, so with a difference of 2 Umol.min.kg FFM, and the standard deviation is 2, with 20 PCOS and 20 controls, we would have a power of 0.87 to detect a alpha of 0.05. b) For comparison of treatment with either metformin or OCP's, we will compare the untreated group to the treatments individually. We will not compare the two treatments to each other. I am assuming that there will be less of a difference between these groups, so with a difference of 2 Umol.min.kg FFM, and the standard deviation is 2, with 30 PCOS and 15 in a treatment group, we would have a power of 0.87 to detect a alpha of 0.05.

All measures will be adjusted for OSA status (yes/no) and/or severity of AHI.

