Overall Expected Results: We anticipate that we will determine which specific areas of hepatic metabolism are upregulated in girls with hepatic steatosis. This data would then provide the background evidence for future therapeutic trials. We will also refine this protocol and identify if metabolomics can be utilized to measure this type of hepatic energy flux.

Significance: Recent evidence in adults with PCOS indicates that 60-70% have NAFLD^{7,15}. Our data shows that > 45% of obese girls with PCOS have NAFLD, likely an underestimate due to exclusion criteria of T2D and weight >250 lbs in the previous protocols. The majority of NAFLD studies have focused on males, and none have been performed in multi-race cohorts of girls with PCOS, despite this high prevalence. NAFLD has been described as the primary driver of worsening metabolic syndrome and CVD in obesity across populations, and can progress to cirrhosis and liver failure^{5,6}. Thus, understanding the relative contributions of adipose and hepatic IR to NAFLD is critical to designing strategies to improve the long term health of these girls and reduce their risk of T2D, CVD and liver failure.

IX. References:

5. de Groot PC, Dekkers OM, Romijn JA, Dieben SW, Helmerhorst FM. PCOS, coronary heart disease, stroke and the influence of obesity: a systematic review and meta-analysis. *Human reproduction update* 2011;17:495-500.

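### Whether the primary hepatic steatosis comparison is adjusted for race and ethnicity hangs on an undefined look at the observed percentages, so the primary analysis is not fixed in advance

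*Combined protocol and SAP*

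**What the plan says.** All of the analysis text is in the combined protocol and SAP, section VII, under the power calculation. The stated primary aim is to compare obese girls with PCOS who have HS with those who do not. The plan gives its reason for considering ethnicity: "as African Americans are less likely to have HS, and Hispanics more likely to have HS". The rule follows in the same sentence: "if ethnicity percentages are different between groups, we will need to adjust for ethnicity in our calculations". It does not say what counts as a difference, how ethnicity is coded, or what model would carry the adjustment. The only between-group tests named are a t test and a Mann-Whitney test, and neither takes a covariate.

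The same section commits to adjusting every measure for sleep apnoea status or severity, with no condition on observed balance.

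On size, the power text assumes "With 15 untreated PCOS with HS and 15 untreated PCOS without HS". Section III.B plans "20 girls with un-treated PCOS" in total, and the enrollment table in section III.C agrees. Section VIII adds: "Our data shows that > 45% of obese girls with PCOS have NAFLD".

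**The concern.** The primary groups are formed by HS status, not by randomisation. If HS is more common in Hispanic girls and less common in African American girls, as the plan says, the two groups differ in race and ethnicity in expectation, whatever one small sample shows. Letting the observed percentages decide has two consequences. The analysis is chosen after the data are seen, and its p-value takes no account of that choice. And if the check is a significance test, groups of 10 to 15 give it little power, so a real imbalance will often pass unadjusted. If race or ethnicity also affects hepatic flux, part of the apparent HS effect would then be a difference in group composition.

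**Working it through.** **Inputs from the documents.** Difference: "the difference between the group means is 3". SD: "and the standard deviation is 2" (both µmol/min/kg FFM). Group size: 15 v 15 in the power text. Twenty untreated girls with HS prevalence just over 45% give about 9 v 11, taken here as 10 v 10. Planned Hispanic share: 40 of 100 (section III.B).

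**Assumptions, not in the documents.** Two-sided alpha of 0.05. Shares of 55% v 30% Hispanic and 20% v 40% Black (HS v no HS), each girl being Hispanic, Black or neither. Hispanic girls have flux higher, and Black girls lower, by γ = 1 to 2 units (0.5-1 SD).

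**Step 1: the plan's power figure.** The plan states: "we would have a power of 0.97 to detect an alpha of 0.05". For a two-sample t test the noncentrality is δ/(σ√(2/n)).
- n = 15: 3/(2√(2/15)) = 4.11 on 28 df, power 0.977. This agrees with the stated 0.97.
- n = 10: 3/(2√(2/10)) = 3.35 on 18 df, power 0.887.

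**Step 2: how often the rule adjusts, one binary factor.** Exact enumeration of two binomials around a 40% Hispanic share:

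| Hispanic share, HS v no HS | n per group | Fisher p ≤ 0.05 | Gap of 20 points or more | Any difference |
|---|---|---|---|---|
| 50% v 30% | 10 | 5% | 65% | 88% |
| 50% v 30% | 15 | 10% | 60% | 92% |
| 60% v 20% | 10 | 25% | 90% | 97% |
| 60% v 20% | 15 | 45% | 92% | 99% |

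With 40% Hispanic overall, Fisher's test needs 7 v 1 of 10, or 10 v 2 of 15, before it triggers.

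**Step 3: both factors, no true HS effect.** The expected unadjusted bias is γ(0.55 − 0.30) + γ(0.40 − 0.20) = 0.45γ, that is 0.45 to 0.90 units. Simulated results by reading of the rule:

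| Reading | Adjusts, 10 v 10 | Adjusts, 15 v 15 | Remaining bias | Type I error |
|---|---|---|---|---|
| Exact test p < 0.05 | 11-12% | 20-23% | about 0.3-0.65 | about 0.06-0.08 |
| Gap of 20 points or more | 84% | 81% | 0.01-0.05 | 0.043-0.050 |
| Any numerical difference | 98% | 99% | 0.00-0.03 | 0.047-0.055 |
| Always adjust | 100% | 100% | 0.00-0.03 | about 0.05 |

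Against the planned difference, 0.3/3 = 10% and 0.65/3 = 22%.

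**Step 4: sensitivity to γ.** With γ = 0 there is no bias under any rule (simulated 0.00-0.01 at 10 v 10). If both shifts ran in the same direction, the expected unadjusted bias would be only γ(0.25 − 0.20) = 0.05γ. The figures in Step 3 are therefore for shifts that compound.

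**Step 5: cost of always adjusting.** If both covariates explain none of the outcome variance, simulated power for a difference of 3 falls from 0.977 to about 0.95 at 15 v 15, and from about 0.89 to 0.81 at 10 v 10. For a single covariate at 60% v 20%, the noncentrality shrinks by √(1 − R²) with R² = 0.2²/(0.4 × 0.6) = 0.167, and power is 0.951 and 0.823 respectively.

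**The case against.** The strongest reply is that the plan mentions no significance test. Read literally, any gap in percentages triggers adjustment. The rule then acts in 98-99% of trials and performs as well as always adjusting. If the observed percentages are exactly equal, these variables do not confound that sample. This stands, and it rules out the inference that ethnicity will usually go unadjusted: that follows only from the significance-test reading with moderate imbalance. It does not rescue the sentence, because the plan does not choose between readings whose adjustment rates differ this widely.

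A reader might also call ethnicity a known confounder. The plan links it to HS and says nothing of an effect on flux apart from HS. It is a plausible confounder, and the 0.5-1 SD shift is assumed.

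A third tempting inference is that adjusting for ethnicity would ignore African American race, since section III.B tabulates ethnicity and race separately. The sentence containing the rule names both groups as its reason, so it evidently means both. In the simulation, adjusting for Hispanic status alone left under a fifth of the bias, although that fraction depends on how the two categories overlap. What remains is that the coding is unstated.

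Finally, the loss of power at 10 v 10 is real, and the calculation covers only the HS contrast. The secondary comparisons use 20 v 20 and 30 v 15, and the comparison with controls is matched on HS.

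**Conclusion.** The point holds as a failure to prespecify the primary HS analysis. The plan gives its own reason to expect the groups to differ in race and ethnicity, then lets an undefined feature of the data decide whether to adjust, while treating sleep apnoea without that condition. The consequence ranges from almost none (any difference triggers) to a bias of about 10-22% of the planned difference with type I error of about 0.06-0.08 (exact test triggers, compounding shifts of 0.5-1 SD). The upper end rests on assumed shares and effects that the documents do not supply. The data-dependence of the rule rests on the text alone.

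**What to change.** Replace the conditional sentence with wording such as: *The primary HS contrast will be estimated from a linear model that includes Hispanic ethnicity (yes/no) and Black/African American race (yes/no) as fixed covariates, whatever their observed balance; the unadjusted result will be shown beside it.* Put the sleep apnoea term in the same model, and state what will replace the Mann-Whitney test if residuals are clearly non-normal, since that test cannot carry covariates.

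The change is to wording only. Section VI lists ethnicity among the demographics collected, and section III.B already tabulates enrollment by ethnicity and race. The price is two degrees of freedom and the power loss in Step 5, before the sleep apnoea term. Any real effect of race or ethnicity on flux would recover some precision. At 10 v 10 the margin over 0.80 is thin, so the group size behind the power statement (30 untreated girls assumed, 20 planned) should be settled at the same time.

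### Secondary aim a) matches PCOS girls to controls on hepatic steatosis (HS), but its power of 0.87 counts all 20 vs 20 girls and allows nothing for unequal HS rates

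*Combined protocol and SAP*

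**What the plan says.** Section VII, Secondary Aims a), says of PCOS girls and controls that "individuals will be matched in terms of HS status, so that the comparison is just between the hormonal state". The same item assumes a difference of 2 and an SD of 2, and concludes: "with 20 PCOS and 20 controls, we would have a power of 0.87". The test for this contrast is named in the power paragraph: "Differences between the two primary groups (PCOS, controls) will be assessed with a t test", or a Mann-Whitney U test for non-normal data. That section also states "All measures will be adjusted for OSA status (yes/no) and/or severity of AHI", and asks for an ethnicity adjustment if the groups differ in ethnicity.

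The number of untreated PCOS girls is not consistent. Section III.B plans "20 girls with un-treated PCOS", and the enrolment table in III.C agrees: 25 screened, then 20 MRIs, 20 overnight stays and 20 tracer studies in each of the four groups. The power paragraph in VII instead counts 30: "With 15 untreated PCOS with HS and 15 untreated PCOS without HS". Secondary Aims b) repeats it: "with 30 PCOS and 15 in a treatment group".

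Section III.B gives the reason for enrolling beyond 20 per group: "thus more subjects may be enrolled, to allow for screen failures and dropouts". Matching is not mentioned there.

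**The concern.** Matching on a characteristic that is more common in one group usually leaves some girls without a partner. The documents expect that here. Section II.b puts fatty liver at 50-70% of obese women with PCOS and 20-30% of obese women without it. Section VIII reports more than 45% in the team's own girls with PCOS. HS is neither an eligibility criterion nor a quota, and controls with fatty liver are eligible, because exclusion 10 removes only liver disease other than NAFLD. The study measures liver fat at the visit 2 MRI, and the number of MRIs planned equals the number of tracer studies.

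So 20 matched girls per group would require every girl to find a match, and the enrolment plan holds no reserve for those who do not. The plan states no ratio, pool or rule for unmatched girls, so 0.87 cannot be tied to a defined analysis. At stake is whether the hormonal contrast has the power claimed, and whether girls who complete a 24-hour inpatient study are then left out of it.

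**Working it through.** **Inputs.** Difference 2, SD 2, alpha 0.05, 20 vs 20 (VII, Secondary Aims a). HS in PCOS 45-70% (VIII for the lower end, II.b for the upper). HS in controls 20-30% (II.b, adult women; no rate is given for control girls). Sidedness is not stated.

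**1. The plan's figure.** Noncentrality = (2/2) × √(20×20/40) = √10 = 3.16, df 38. Two-sided power is 0.869, which is the stated 0.87. One-sided power would be 0.928. The figure therefore uses all 40 girls, unpaired.

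**2. Matching.** Assumed, not stated in the plan: 1:1, without replacement, unmatched girls dropped. With a PCOS girls (of nP) and b controls (of 20) having HS:

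pairs = min(a, b) + min(nP − a, 20 − b)

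Examples at expected counts with nP = 20:
- 45% vs 30%: a = 9, b = 6, so 6 + 11 = 17 pairs, power 0.807.
- 70% vs 20%: a = 14, b = 4, so 4 + 6 = 10 pairs, power 0.562.

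Letting a and b vary binomially and averaging the two-sample power:

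| HS, PCOS / control | 20 PCOS: pairs, power | 30 PCOS: pairs, power |
|---|---|---|
| 45% / 20% | 14.9, 0.739 | 18.9, 0.846 |
| 45% / 30% | 16.5, 0.786 | 19.5, 0.859 |
| 60% / 20% | 12.0, 0.635 | 15.8, 0.764 |
| 60% / 30% | 13.9, 0.706 | 17.4, 0.808 |
| 70% / 20% | 10.0, 0.549 | 13.0, 0.671 |
| 70% / 30% | 12.0, 0.634 | 14.9, 0.736 |

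With 20 vs 20, all 20 girls can be paired in at most 8% of cases (45% / 30%). If the 30 untreated girls are fixed at 15 with HS and 15 without, there are 18.7-19.6 pairs and power is 0.84-0.86.

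**3. Adjusting for HS instead.** In a linear model on PCOS and HS, every girl is kept. The noncentrality is √[nP×20/(nP+20) × (1 − R²)], where R² is the squared correlation between PCOS and HS, with df = nP + 17. For 20 vs 20 at expected counts:
- 9 vs 6 with HS: R² = (9×14 − 6×11)²/(20×20×15×25) = 3600/150000 = 0.024.
- 14 vs 4 with HS: R² = (14×16 − 4×6)²/(20×20×18×22) = 40000/158400 = 0.253.

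Averaged over chance counts with residual SD 2:
- 20 vs 20: 0.735 (70% / 20%) to 0.850 (45% / 30%).
- 30 vs 20: 0.823 to 0.912, or about 0.89-0.91 with the 15/15 split fixed. Part of this gain comes simply from using all 30 girls.

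**The case against.** The strongest reply is that the plan never says girls will be dropped. Frequency matching at selection, a variable ratio or an HS-stratified comparison would discard few or none. That stands, and it makes the matching loss conditional. It does not rescue 0.87 for 20 vs 20, because HS adjustment without discarding anyone still gives 0.74-0.85 when HS and PCOS are correlated.

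A second reply is that the 20 PCOS girls may be chosen from the 30 untreated girls counted in the same section. On that reading, with the 15/15 split, matched power is 0.84-0.86, a loss of 1-3 points. This also stands, but III.B and the enrolment table supply only 20 untreated girls. Using all 60 PCOS girls would nearly remove the loss (19.2-20.0 pairs, 0.85-0.87). However, 40 of them are on metformin or oral contraceptives, which sits poorly with isolating the hormonal state.

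Third, HS status may already be known for some girls, since the recruitment plan allows re-contact of participants from earlier protocols and liver fat was measured in at least one of them. No selection of girls by HS is described, however.

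Fourth, matching might gain precision through similarity within pairs. The documents give no such correlation. The SD of 2 comes from a comparison of men with and without HS; if it is a within-group SD, no gain is expected.

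A reader might infer that the true power is about 0.55. The documents do not support that: it needs the adult extremes (70% vs 20%), the smaller pool and the discarding of unmatched girls, all together.

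**Conclusion.** The point holds in conditional form. The arithmetic of 0.87 is right for an unpaired comparison of 20 vs 20, but the plan describes a different, HS-matched comparison and does not define it. With 20 untreated PCOS girls, residual SD 2 and the HS rates assumed above, 0.87 is too high whether girls are matched 1:1 with discarding (0.55-0.79; 0.74-0.79 at 45% HS in PCOS) or HS is adjusted for (0.74-0.85). With 30 untreated girls, matching gives 0.67-0.86, from clearly short to about right, and adjustment gives 0.82-0.91. The control HS rate is an adult figure applied to girls, which is the weakest input. This is a secondary comparison, so the point is a change worth making and does not undermine the study as a whole.

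**What to change.** 1. Reconcile 20 with 30 untreated PCOS girls across III.B, the III.C enrolment table and VII, and state which PCOS girls enter this comparison.
2. Replace matching, and the plain t test for this contrast, with a linear model of the flux outcome on PCOS status, HS (yes/no, using the fat fraction above 5.5% given with the preliminary sleep data), the OSA term already required, and ethnicity if the groups differ. Include every eligible girl. For non-normal outcomes, use a transformation or a rank-based version of the same model in place of Mann-Whitney.
3. Restate the power before the OSA and ethnicity terms, with the HS assumptions shown: about 0.74-0.85 for 20 vs 20, or 0.82-0.91 for 30 vs 20 (about 0.89-0.91 with a fixed 15/15 split).
4. If matching is kept, state the ratio, the pool, the handling of unmatched girls and the power at the expected number of pairs.

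The cost is wording and a restated power. The MRI is already planned for all 80 girls, so steps 2-4 need no new participants or procedures. A small downside is that the model assumes a similar PCOS effect with and without HS. With about 4-6 HS-positive controls (20-30% of 20), that can be checked only descriptively.
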